### **3.2 Study Population**

32 healthy male or female volunteers 18 to 55 years old and with a body mass index (BMI) between 18 and 35 kg/m^2 will be randomized.

### **3.3 Randomization and Treatment Assignments**

This study will be double-blind and placebo-controlled. There will be 4 SAD cohorts. Eight subjects will be enrolled into each of the 4 dosing cohorts. Subjects in each cohort will be randomized at a ratio of 3:1 to receive RGLS8429 or placebo. In each cohort, 6 subjects will be randomized to receive RGLS8429 and 2 will be randomized to receive placebo.

ICON will provide a randomization schedule and eligible subjects will be randomized sequentially to receive the study drug assigned to the corresponding randomization number. Subjects may be randomized once all Screening and Day -1 procedures have been completed and eligibility has been confirmed by the Investigator. Details regarding randomization procedures will be provided in the study reference manual.

Enrollment into subsequent cohorts will be initiated after review of safety (AEs and safety laboratory tests) from the prior cohort. The investigator or a designee will assign sequential subject identification numbers to the subjects as they are screened and enrolled in the study.

An unblinded pharmacist will be responsible for preparing RGLS8429 or placebo and providing the study drug to blinded study personnel for administration according to the Pharmacy instructions within the Study Reference Manual.

### **3.4 Determination of Sample Size**

Formal sample size calculations were not performed for this study. The dose cohort size is 8 subjects randomized 3:1 to RGLS8429 versus placebo. The size of each dose cohort was chosen to provide sufficient information to allow assessment of the safety and tolerability of RGLS8429.

#### **4 CHANGES IN THE CONDUCT OF THE STUDY OR PLANNED ANALYSIS**

All analyses specified in this SAP are consistent with the final study protocol (Version 3.0, dated 06 June 2022). Any changes in the analyses provided or any additional analyses performed will be documented in the clinical study report (CSR).

## **5 QUALITY CONTROL AND QUALITY ASSURANCE METHODS FOR DATA ANALYSIS**

Case report forms will be reviewed and processed according to the ICON Study Specific Procedure SSP DM-38770009.01 Data Management Plan (DMP). The DMP describes eCRF data processing, edit checks, data query management, medical dictionary coding, SAE reconciliation, data transfers, and data quality review through database lock or any necessary reopening of the database. After database lock, the data will be retrieved from the database using SAS version 9.4 or higher. Independent programming will be performed for the analysis. Statistical review should be conducted on an ongoing basis as each output passes validation after lead programmer review or at one-time point only when all outputs have been validated. When statistical review is performed and completed, the Lead Statistician, Programming lead and Project lead will sign a Biostatistics and Programming Validation and Release Form (refer to PRG001-SOP) to verify that all applicable procedures and review steps have been performed and authorizing the release of TLFs.

## 6 PHARMACOKINETIC AND PHARMACODYNAMIC ASSESSMENTS

### 6.1 Pharmacokinetic Assessment

Plasma concentrations of unchanged RGLS8429 at different time-points and urine concentrations collected over the specified interval will be used to derive the following PK parameters using non-compartmental methods (Phoenix™ WinNonlin®, Version 8.0 or later higher, Certara, Princeton, NJ)

The following PK parameters will be reported:

| Variable            | Definition                                                                                                                                          |
|---------------------|-----------------------------------------------------------------------------------------------------------------------------------------------------|
| AUC 0-24 | Area under the plasma concentration-time curve from time =0 to 24 estimated using the linear/log trapezoidal rule                                   |
| AUC 0-t  | Area under the plasma concentration-time curve from time =0 to the last quantifiable concentration estimated using the linear/log trapezoidal rule. |
| AUC inf  | Area under the plasma concentration-time curve extrapolated to infinite time calculated as:                                                         |

$$AUC_{inf} = AUC_{0-t} + \frac{C_{last}}{\lambda_z}$$

Where Clast is the last observed quantifiable concentration, and λz is the terminal rate constant for elimination.

|                  |                                                                                                                                                                               |
|------------------|-------------------------------------------------------------------------------------------------------------------------------------------------------------------------------|
| C max | Maximum observed plasma concentration.                                                                                                                                        |
| T max | Time to C max . If the maximum observed concentration value occurs at more than 1 time point, T max is defined as the first time point with this value. |
| t 1/2 | Terminal elimination half-life in plasma computed as:                                                                                                                         |

$$t_{1/2} = \frac{\ln(2)}{\lambda_z}$$

Where ln(2) is the natural logarithm of 2.

|      |                                                                 |
|------|-----------------------------------------------------------------|
| CL/F | Apparent total clearance of the drug from plasma calculated as: |
|      | $CL / F = \frac{Dose}{AUC_{inf}}$                               |

|                   |                                                                             |
|-------------------|-----------------------------------------------------------------------------|
| V z /F | Apparent volume of distribution during the elimination phase calculated as: |
|                   | $V_z / F = \frac{Dose}{\lambda_z \cdot AUC_{inf}}$                          |

| Variable    | Definition                                                                                                                                                                                                                                                                                                                                                   |
|-------------|--------------------------------------------------------------------------------------------------------------------------------------------------------------------------------------------------------------------------------------------------------------------------------------------------------------------------------------------------------------|
| $Ae_{0-24}$ | Total amount of unchanged RGLS8429 excreted in the urine after the first dose of RGLS8429 (Day 1):
$Ae_{t_1-t_2} = Cu_{t_1-t_2} \cdot Vu_{t_1-t_2}$ Where $Cu_{t_1-t_2}$ is the concentration in urine collected over the interval from time 0 to 24 hours and $Vu_{t_1-t_2}$ is the volume of urine collected over the interval from time 0 to 24 hours. |
| $fe_{0-24}$ | Fraction of the unchanged drug excreted in urine over the interval from time $t_1$ to time $t_2$ computed as:
$fe_{0-24} = \frac{Ae_{0-24}}{Dose}$                                                                                                                                                                                                        |
| $CL_R$      | Renal Clearance computed as:
$CL_R = \frac{Ae_{0-24}}{AUC_{0-24}}$                                                                                                                                                                                                                                                                                        |

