1.3. Nonclinical Pharmacokinetics, Pharmacology, and Toxicology

The following is a brief summary of the Nonclinical information. Please see the RGLS8429 Investigator's Brochure for a more detailed presentation of this information.

In nonclinical ADPKD efficacy studies, RGLS8429 treatment reduced disease progression in both *Pkd1*^{F/RC} and *Pcy*/DBA mouse models. In the *Pkd1*^{F/RC} mouse model, RGLS8429 caused a significant reduction in kidney weight-to-body weight ratio, serum blood urea nitrogen (BUN), kidney cyst index, and kidney cyst proliferation. In the *Pcy*/DBA mouse model, RGLS8429 reduced kidney weight-to-body weight ratio significantly. In addition, the combination of RGLS8429 and tolvaptan demonstrated a greater reduction in disease progression than either drug alone in the *Pcy*/DBA mouse model.

Based on in silico bioinformatics analysis and in vitro receptor binding studies, RGLS8429 appears to have low potential for off-target effects towards ribonucleic acid (RNA) and receptor targets.

RGLS8429 had no effects on cardiovascular, respiratory, and central nervous system function at supraclinical concentrations and dose levels in animals. RGLS8429 had no meaningful effect on the human ether-à-go-go-related gene (hERG) potassium channels in vitro.

In nonclinical PK and toxicokinetic studies, SC administration of RGLS8429 demonstrated rapid absorption (time to maximum concentration [T_{max}] 1-2 hr) followed by relatively rapid plasma clearance. The plasma $t_{1/2}$ in mice (~ 2 hr) whereas $t_{1/2}$ ranged between 6 -7 hr in monkeys.

Plasma exposure increased in a generally dose-proportional manner across all dose levels, and no meaningful accumulation was observed in mice or monkeys. RGLS8429 is highly bound to plasma protein in mice, monkeys and humans, monkeys, and mice (79.1% ,86.6%, and 81.6 %, respectively). RGLS8429 distributes rapidly to the kidney and liver, is metabolically stable with only trace amounts of metabolites measured, and is excreted rapidly in the urine, primarily in the first 24 hours after dosing. Of note, the decreased renal function present in patients with ADPKD is expected to decrease the renal clearance of RGLS8429, and therefore, will be monitored closely in clinical trials.

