2.2. Study Endpoints

Primary Endpoint

- Incidence of adverse events (AEs) and change in safety laboratory test results, vital signs, SARA, and ECG parameters and Holter monitoring over time

Secondary Endpoints

- Incidence of DLT and determination of MTD
- PK parameters of RGLS8429 including:
 - Maximum observed concentration (C_{max})
 - Time to maximum observed concentration (T_{max})
 - Area under the concentration–time curve up to 24 hr post dose (AUC_{0-24})
 - Area under the concentration–time curve up to the last quantifiable concentration (AUC_{0-t})
 - Area under the concentration–time curve extrapolated to infinity (AUC_{inf})
 - Half-life ($t_{1/2}$)
 - Apparent clearance (CL/F)
 - Volume of distribution (V_z/F)
 - Fraction of unchanged RGLS8429 excreted in the urine (fe)
 - Total amount of unchanged RGLS8429 excreted in the urine (Ae)

Exploratory Endpoints

- Characterize multiple potential renal biomarkers in urine (e.g., PC2, NGAL, KIM-1, MCP-1, B2M, and CLU) and in serum (e.g., Cystatin-C, IGFALS, Alb, CT-proAVP, N-acetyl-1-methylhistidine, and others)

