5.2. Treatment Period (Day 1 and Day 2)

The following procedures are to be performed on Day 1 and/or Day 2:

- Limited physical examination (pre-dose Day 1 and 24 hr post-dose Day 2)
- Vital signs (Day 1 pre-dose and 1, 2, 4, and 8 hr post-dose; Day 2, 24 hr post-dose)
- Holter monitoring should be initiated 1 hr pre-dose and continue for approximately 30 minutes after the 24-hr PK sample is obtained (Day 1 and Day 2).
- Print and review ECG tracings pre-dose and 4, 6, 12, and 24 hr post-dose.
- SARA assessment (Day 1 pre-dose and 4-6 hr post-dose; Day 2, 24 hr post-dose)

Note: The pre-dose ECG tracing and SARA procedures may be performed prior to the start of Holter monitoring at the 1 hr pre-dose timepoint on Day 1.

- Safety laboratory tests (Day 2, 24 hr post-dose):
 - Hematology
 - Chemistry
 - Urinalysis
 - Lipids
- Coagulation test (Day 1, 4 hr post-dose and Day 2, 24 hr post-dose)
- AE monitoring (Day 1 through Day 2)
- Concomitant medications and procedures (Day 1 through Day 2)
- Study drug administration (Day 1 at Time Zero)
- PK plasma samples (Day 1 pre-dose and 2, 4, 6, 8, and 12 hr post-dose; Day 2, 24 hr post-dose. Pre-dose plasma PK sample on Day 1 should be obtained within 60 minutes prior to dosing. Post-dose plasma samples should be obtained within the following time margins: collections at 2, 4, 6, and 8 hr \pm 15 minutes, 12 hr \pm 30 minutes, and 24 hr \pm 60 minutes.)
- 24-hr urine collection on Day 1 and Day 2 for PK analysis will begin immediately after study drug dosing on Day 1 (0-24 hr). The subject should void immediately before dosing and at the end of the 24-hr collection period.
- Discharge from clinic (Day 2) no less than 6 hr after the 24-hr PK sample collection

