5.3.2. Follow-Up Visit (Day 15)

The following procedures are to be performed on Day 15:

- Limited physical examination; must include a complete neurologic examination
- Vital signs
- Safety laboratory tests:
 - Hematology
 - Chemistry
 - Urinalysis
 - Lipids
- AEs since the last visit
- Concomitant medications and procedures since last visit
- Plasma PK sample

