### 6.1.2 Non-Quantifiable Concentrations

All concentration values reported as no results (not collected or not determined) values will be treated as missing. For the calculation of concentration summaries, all concentrations below the quantifiable limit (BLQ) will be treated as 0. For the purpose of calculating PK parameters and plotting mean and individual concentration-time profiles, BLQ values will be treated as 0 prior to the first measurable concentration. After the first measurable concentration, subsequent BLQ values (or mean concentration values that are BLQ) are treated as missing.

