Additional PK parameters may be estimated as appropriate. The parameters stated above will be reported if they are estimable and will be discussed in the CSR. When necessary, interpolation or  $\lambda_z$  extrapolation may be used to estimate partial AUCs. The value of  $AUC\%_{extrap}$  will be less than or equal to 20% for the  $AUC_{inf}$  to be considered well estimated. If this proportion is > 20%, then the values of  $AUC_{inf}$  will be treated with caution. When  $AUC_{inf}$  is calculated and tabulated, the  $AUC\%_{extrap}$  will also be tabulated. Where  $AUC\%_{extrap} > 20\%$ ,  $AUC_{inf}$  and all related parameters (i.e. CL/F and Vz/F) will be presented but excluded from the calculation of summary statistics. All values excluded from the summaries should be flagged in the individual listings with an explanation for the exclusion.

The apparent terminal phase rate-constant ( $\lambda_z$ ) will be estimated by log-linear regression of the concentration-time data associated with this phase. The decision as to which data points describe the terminal phase will be reached by inspecting the semi-logarithmic plot of the data, only considering concentrations at time points beyond  $T_{max}$ . A minimum of three data points will be used for the estimation of  $\lambda_z$  preferably covering a time span of at least 2 half-lives. Poorly estimated  $\lambda_z$  (i.e. if a time span of at least 2 half-lives is not used or  $r^2_{adj} \leq 0.80$ ), the corresponding  $t_{1/2}$  and other parameters derived using  $\lambda_z$  (i.e.  $AUC_{inf}$ , CL/F, Vz/F, and  $t_{1/2}$ ) will be flagged in the report. Summary statistics of these parameters (i.e.  $AUC_{inf}$ , CL/F, Vz/F, and  $t_{1/2}$ )

will be reported with and without these outliers (i.e., with and without parameters where  $\lambda_z$  was poorly estimated).

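### Does the SAP need a special rule for the Day 15 plasma PK sample so that AUC0-t does not end at 24 h in some subjects and 336 h in others?

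*SAP*

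**What the plan says.** Protocol 5.2 lists "PK plasma samples (Day 1 pre-dose and 2, 4, 6, 8, and 12 hr post-dose; Day 2, 24 hr post-dose". The Day 8 visit list has no PK draw. Protocol 5.3.2 then lists a "Plasma PK sample" on Day 15. The PK rows of the schedule tables are not legible in the text available, so the Day 15 draw rests on section 5.3.2.

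Protocol 2.2 defines AUC0-t as the area under the "time curve up to the last quantifiable concentration". SAP 6.1 repeats this: "Area under the plasma concentration-time curve from time =0 to the last quantifiable concentration estimated using the linear/log trapezoidal rule". AUCinf adds the last quantifiable concentration divided by lambda-z; CL/F and Vz/F follow from AUCinf.

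SAP 6.1.2 adds: "After the first measurable concentration, subsequent BLQ values (or mean concentration values that are BLQ) are treated as missing". SAP 7.2 lets the trapezoid bridge missing values. In SAP 7.15, "A minimum of three data points will be used for the estimation of" lambda-z. The points come from the semi-log plot beyond Tmax, and fits are flagged if adjusted r2 is 0.80 or less or the span is under 2 half-lives. AUCinf is left out of summaries when more than 20% is extrapolated. The power model is fitted to Cmax, AUCinf, AUC0-24 and AUC0-t.

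No SAP analysis section names Day 15, and the sampling windows in the Table 3-1 footnote stop at 24 h.

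**The concern.** Under the general rules, a quantifiable Day 15 value takes AUC0-t to 336 h, and a value below quantification drops it back to 24 h or earlier. Nothing is sampled in the 312 h between. If quantifiability rises with dose across the 8-fold range, the horizon changes with the regressor of the power model, and the AUC0-t slope can leave 1 although exposure is proportional. A single log trapezoid also overstates the area when a fast decline is followed by a slow tail. A lambda-z line through 12, 24 and 336 h would then describe neither phase. AUC0-t, AUCinf, t1/2, CL/F and Vz/F are all secondary endpoints, and whether Day 15 counts would be settled only once the profiles are seen.

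**Working it through.** The plan states no AUC or power figure to reproduce, so the check has three steps.

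**1. Is Day 15 likely to be quantifiable?** Nominal time is (15 - 1) x 24 = 336 h; the gap is 336 - 24 = 312 h. Protocol 1.3 gives a plasma half-life of about 2 h in mice and one that "ranged between 6 -7 hr in monkeys", with urinary excretion mainly in the first 24 hours. With a single phase, C336/C24 = 2^(-312/t1/2):
- 7 h: 2^(-44.6), about 4e-14
- 6 h: 2^(-52), about 2e-16
- 2 h: 2^(-156), about 1e-47

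The documents give no assay limit and no human half-life. On these half-lives Day 15 is below quantification in everyone, SAP 6.1.2 makes it missing, and the effect is zero.

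**2. What if there is a slow phase?** Everything in this step is assumed except the 2 h and 6.5 h half-lives, which are nonclinical values. C(t) = exp(-kt) + B exp(-kb t), absorption ignored, slow half-life 168 or 336 h, and B set so that C336/C24 is 0.1%, 1% or 5%. The trapezoid is (C24 - C336) x 312 / ln(C24/C336).

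One case (6.5 h fast, 168 h slow, 5%), with the fast-phase intercept as 1:
- C24 = 0.0945, so the trapezoid is 0.0945 x 0.95 x 312 / ln 20 = 9.35, against a true area of 3.73.
- AUC0-24 = 9.08. The sum is 18.43 against a true 12.81, which is 44% too high and 2.03 times AUC0-24.

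Dose levels are ln 2 apart, so if only the top two cohorts run to 336 h the slope shifts by 2 ln(ratio)/(5 ln 2). Here that is 2 x 0.708/3.466 = 0.41. SAP 7.15 uses actual dose in mg, so equal spacing is an approximation. Over the grid:

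| Fast t1/2 | AUC0-t overstatement | Slope, top two cohorts only |
|---|---|---|
| 2 h | 0.4-0.7% | 1.002-1.006 |
| 4 h | 10.5-20% | 1.07-1.16 |
| 6.5 h | 29-51% | 1.20-1.41 |

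For scale, the slope SE at an assumed CV of 30% and n = 24 is sqrt(ln 1.09)/sqrt(24 x 1.25 x (ln 2)^2) = 0.077. The shift is zero if Day 15 is quantifiable in all four cohorts or in none.

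**3. Would ending the analysis at 24 h be better?** Error in AUCinf against the true value at a 6.5 h fast half-life:

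| C336/C24 | With Day 15 (12/24/336 h fit) | Through 24 h only (8/12/24 h fit) |
|---|---|---|
| 0.1-5% | 29-39% high | 0.7-28% low |
| 10% | 17-23% high | 46-47% low |

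For ratios of 0.1-5%, neither fit is flagged. With Day 15, adjusted r2 is 0.88-0.975, the span is 5.3-11.1 half-lives and extrapolation is at most 2.2%. Through 24 h, adjusted r2 is at least 0.9997, the span is 2.2-2.5 half-lives and extrapolation is at most 9.7%.

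**The case for a change.** The strongest case for acting is that the gap can be checked in the text and that the SAP's quality checks would miss it where it matters most. At a 6.5 h fast half-life the 12/24/336 h fit passes all three checks, yet reports a half-life of 29-61 h, which matches neither phase. The slope shift there is roughly 2.5 to 5 standard errors. Fixing the convention beforehand would cost a few sentences.

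The silence is real, and so is the weakness of the checks in that scenario. Three things limit what follows.

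- The scenario needs a slow phase that appears nowhere in the documents. The slope figures also need every subject to switch exactly at a cohort boundary.
- General rules do cover the sample. A horizon set by quantifiability is the protocol's own definition of AUC0-t, not an omission. Forcing it to 24 h would be a change of endpoint, at odds with SAP Section 4 ("All analyses specified in this SAP are consistent with the final study protocol"), and would leave AUC0-t largely a copy of AUC0-24.
- The effect would not stay hidden. Concentrations are listed and summarised by nominal time, each subject has a semi-log plot, and the Cmax and AUC0-24 slopes would disagree with the AUC0-t slope.

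**Conclusion.** No change to the plan is needed. The SAP does not say whether Day 15 enters AUC0-t, lambda-z or AUCinf, but on the half-lives the protocol reports the question does not arise. If a slow phase exists, the size depends wholly on assumptions: under 1% in AUC0-t at a 2 h fast half-life, and 29-51% at 6.5 h. Neither inclusion nor truncation is uniformly better. At 6.5 h truncation gives the smaller AUCinf error for C336/C24 up to 5% and the larger one at 10%, so imposing a 24 h cut-off in advance has no clear gain.

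The plan already holds what a reader needs: AUC0-24 as a fixed-horizon endpoint and power-model response, and full display of concentrations. Dose proportionality is exploratory with no decision rule, and the primary endpoint is safety. If any Day 15 value proves quantifiable, a careful pharmacokineticist would see it on the plot and give AUC0-t, AUCinf and t1/2 with and without it. SAP Section 4 already lets such additional analyses be documented in the study report. The conclusion rests on human disposition being roughly as fast as the nonclinical data suggest, which the documents cannot confirm.

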### 6.1.1 Treatment of Outliers

Individual concentration-time points, if considered anomalous, may be excluded from the analysis at the discretion of the pharmacokineticist following a review of the available documentation. Any such exclusion will be discussed with the sponsor and clearly outlined in the study report.

Entire individual treatment profiles for a subject may be excluded following review of the available documentation and discussion with the sponsor. However, results of analysis with and without the excluded profiles may be presented in the study report. Any such exclusion will be clearly listed in the study report along with justification for exclusion.

